1.1 Background and rationale

Statin non-adherence (i.e. patients not taking their prescribed drugs) remains a major public health concern in cardiovascular disease patients, leading to adverse outcomes in terms of morbidity, mortality and healthcare costs¹⁻³. The principal reason for statin non-adherence and discontinuation is statin-associated muscle symptoms (SAMS)⁴. SAMS, comprising a heterogeneous group of muscle symptoms including pain/aching, stiffness, tenderness or cramps, usually with normal or minimally elevated creatinine kinase levels, is prevalent challenge in clinical practice⁴. In contrast, serious statin side-effects, including liver failure, rhabdomyolysis, or myositis with elevated creatinine kinase levels in blood, are very rare^{4,5}. In randomized trials, statin therapy appears to cause only a slightly increased risk of side-effects of 1-5% compared with placebo, far below the prevalence reported in clinical practice, amounting to 30% in observational studies^{6,7}. Strict entry criteria in the randomized statin trials, excluding patients with polypharmacy, multiple comorbidities, elderly, females and low body weight, factors that predispose to musculoskeletal symptoms, may in part explain the diverging frequency of SAMS⁴. A major limitation of observational studies is a lack of blinding. Patients on statins may expect to experience side-effects, and therefore report a higher percentage than in a comparable population not on statins, the so-called 'nocebo' effect. Two previous studies, in subjects without cardiovascular disease, has tested whether SAMS reported by the patients are related the statin therapy⁸⁻⁹. In a randomized, double-blind crossover study that included patients complaining of SAMS at study start, only 36% experienced that their muscle symptoms persisted during treatment with simvastatin 20 mg and disappeared during placebo treatment⁸. Accordingly, SAMS was confirmed to be related to the statin treatment in one-third of the patients. The proportion of CHD patients with confirmed SAMS, treated with potent statins recommended for these patients, remains unknown. Furthermore, the clinical presentation (i.e. location, intensity and characteristics) of the muscle symptoms in CHD patients with and without confirmed SAMS remains to be investigated.

Although several mechanisms have been proposed, it remains unclear how statins produce muscle symptoms, and reliable diagnostic biomarkers for the prediction or diagnosis of SAMS are lacking^{4,5}. For patient follow-up it is highly relevant to identify markers that predict the occurrence of muscle symptoms, and thus enable preventive actions. Individual variations in statin pharmacokinetics, mitochondrial dysfunction or coenzyme Q10 deficiency are suggested mechanisms for SAMS^{4,5}. A few observation studies indicate that pharmacokinetic alterations in statin metabolites may contribute to SAMS^{10,11}. The lactone metabolites of statins seem to be most potent in inducing myotoxic effects compared to the corresponding acid metabolites¹⁰. Accordingly, plasma concentrations of atorvastatin lactones have been associated with clinical muscle symptoms¹¹. In the present project we will determine the relationship between muscle symptoms and blood levels of atorvastatin metabolites using our liquid chromatography mass spectrometry method¹². Importantly, we have pilot data indicating significantly higher levels of atorvastatin lactone metabolites (sufficient for statistical significance) in patients reporting subjective SAMS, compared with those not reporting muscle symptoms¹³. If statin metabolite levels prove to be significantly stronger correlated with subjective muscle symptoms in patients with confirmed SAMS compared to those without in a randomized placebo-controlled study, this may pave the way for diagnostic testing of confirmed SAMS.

STATISTICAL ANALYSIS PLAN for MUscle Side-Effects of atorvastatin in coronary patients (MUSE) – a randomized controlled trial

1.2 Trial Objectives

1.2.1 Primary Objective

To estimate the effect of atorvastatin on muscular symptom intensity in coronary patients with subjective SAMS.

1.2.2 Secondary Objectives

The secondary objectives of this study are:

- To determine the proportion of patients who report muscle symptoms on atorvastatin treatment compared with on placebo (dichotomous SAMS classification)
- To determine the correlation between muscular symptom intensity and blood concentrations of parent drug and metabolites of atorvastatin in patients with confirmed SAMS*
- To determine the diagnostic properties of blood concentrations of parent drug and metabolites of atorvastatin for classification of confirmed SAMS*
- To determine adherence to the study medication (i.e. atorvastatin and placebo) during the treatment periods
- To compare blood concentrations of parent drug and the metabolites of atorvastatin between patients with failing placebo-test (i.e. non-SAMS)* for connecting SAMS to atorvastatin and the control group without muscle symptoms
- To describe study safety

**Confirmed SAMS is defined as at least $\geq 25\%$ higher mean muscle symptom intensity (measured on a 0-10 cm Visual Analogue Scale [VAS]) and a 1cm difference during the last 3 weeks on treatment with atorvastatin compared to placebo. All other patients in the are defined as non-SAMS.*

1.2.3 Exploratory Objectives

The exploratory objective of this study is:

- To compare patients with and without confirmed SAMS regarding muscle symptom characteristics and location
- To study sociodemographic, clinical, and psychosocial characteristics (PROMS and clinical data) in patients with and without confirmed SAMS

2 Trial Methods

[figure not shown]
2.1 Trial Design

MUSE is a randomized, double-blinded, multi-center, cross-over phase 4 study in Norway that aimed to include 80 CHD patients with subjective SAMS during atorvastatin therapy who report i) ongoing SAMS or ii) atorvastatin discontinuation because of SAMS. The patients will be randomized 1:1 to either atorvastatin in the first period and placebo in the second period or placebo in the first period and atorvastatin in the second period, in an AB/BA cross-over design. (Figure 1) In addition, 40 coronary patients on atorvastatin (at least 40 mg) but without SAMS at the time of inclusion in the

STATISTICAL ANALYSIS PLAN for MUScle Side-Effects of atorvastatin in coronary patients (MUSE) – a randomized controlled trial

study will be included consecutively and undergo an open 7 weeks treatment period with atorvastatin in a similar dose as in those with subjective SAMS.

Figure 1. Study flow-chart

2.2 Randomisation

Eligible patients will be randomized to double-blinded prescription of atorvastatin or a matched placebo tablet in a 1:1 ratio using the electronic randomisation system (Viedoc™) of the Clinical Trials Unit (CTU) at Oslo University Hospital. Block randomization with block size 4 and 6 in random order, stratified according to centre (Drammen Hospital and Hospital of Vestfold) and previous atorvastatin discontinuation (yes/no), will be used.

The randomization process is described in full within the clinical trial protocol. Details of the randomization including the final random allocation list are held securely and unavailable to unauthorized trial personnel.

2.3 Sample size

Sample size calculations are based on our being able to detect a 1 cm difference in the VAS symptom score between the treatment periods on atorvastatin and placebo since the smallest change in VAS symptom score corresponding to ‘a little more’ or ‘a little less’ symptoms was 1.3 cm, with a lower limit of the CI at 1 cm in a previous study by Gallagher et al¹⁴. Gallagher et al. report a standard

STATISTICAL ANALYSIS PLAN for MUScle Side-Effects of atorvastatin in coronary patients (MUSE) – a randomized controlled trial

deviation (SD) of 1.7 for a difference of 1.0 between two VAS symptom scores. Because of the differences in both populations and specific VAS scale between that study in this one, we use SD=2.5 to account for a much larger variation in this study. With n=68, we will have 90% power to detect a difference of 1.0, using a one-sample T test. With n=68, we will also have 80% power to detect a difference of 40% SAMS under statins vs. 15% SAMS under placebo, using the McNemar test for paired probabilities. To account for some missing information due to drop-outs or and protocol deviations, we plan to include 80 patients.

2.4 Statistical Framework

2.4.1 Hypothesis Test

This study is designed to detect that the reported SAMS under atorvastatin treatment is higher (corresponding to at least “a **little more***” symptoms) than under placebo treatment.

- The primary null hypothesis is that the level of reported SAMS is equal under atorvastatin and placebo treatment.
- The primary alternative hypothesis is that there is a difference in the level of reported SAMS between atorvastatin and placebo treatment.

There is only one identified primary analysis in this trial. All other efficacy analyses will be regarded as supportive or exploratory.

* See Section 2.3

2.4.2 Decision Rule

This trial is designed to address a single primary outcome. Higher SAMS under either atorvastatin treatment or placebo treatment is claimed if the primary null hypothesis is rejected at the 5% (alpha = 0.05) significance level (two-sided).

2.5 Statistical Interim Analyses and Stopping Guidance

There will be no interim analyses in this trial.

2.6 Timing of Final Analysis

The main analysis is planned when all patients have concluded 16 weeks of treatment, all data up to 16 weeks have been entered, verified and validated and the primary database has been locked.

2.7 Timing of Outcome Assessments

For all clinically planned measures, visits should occur within a window of the scheduled visit. Visits outside visit window is regarded a protocol deviation. The target day and visits window are defined in the protocol as:

STATISTICAL ANALYSIS PLAN for MUScle Side-Effects of atorvastatin in coronary patients (MUSE) – a randomized controlled trial

Visit Label	Target Day	Definition (Day window)
Screening	Day -60 to -1	Prior to Day 0
V1. Baseline	Day 0 (Randomization)	Day 0
V2	56**	Target day \pm 2 days
V3	112**	Target day \pm 2 days
Last study visit*	112**	112

*The last study visit is defined as the visit following the last visit with randomised treatment, and where there is a study end statement.

**According to the protocol, V2 and V3 (last visit) may be scheduled after a treatment period of at least three consecutive study weeks (21 days) in participants with intolerable muscle complaints.

For analysis and tabulation purposes, we define study time points as

Time Point Label	Target Day	Definition (Day window)
TP1. Baseline	Day 0 (Randomisation)	Information up to randomisation
TP2. Week 8	56	Days 1 to 56
TP3. Week 16	112	Days 56 to 112

If more than one visit fall into the same time point interval, information on all visits will be used in the analyses.

3 Statistical Principles

3.1 Confidence Intervals and P-values

All calculated P-values will be two-sided and compared to a 5% significance level. If a P-value is less than 0.05, the corresponding treatment difference will be denoted as statistically significant. All efficacy estimates will be presented with two-sided 95% confidence intervals. As there is only one primary null hypothesis to be tested in this trial, there will be no adjustments for multiplicity.

3.2 Adherence and Protocol Deviations

3.2.1 Adherence to Allocated Treatment

Adherence to study treatment is based on both **indirect** and **direct** methods:

Indirect method:

Adherence for each patient is based on pill counts in returned containers. It is defined as:

STATISTICAL ANALYSIS PLAN for MUScle Side-Effects of atorvastatin in coronary patients (MUSE) – a randomized controlled trial

% adherence = proportion of days covered (PDC) = $(1 - \text{number of remaining pills}/\text{number of pills delivered to patient}) \times 100\%$

Low adherence = PDC <80% in at least one of the two treatment periods.

Mean (SD) PDC and the proportion of patients with PDC <80% will be presented for all patients and stratified for (i) treatment order allocation and (ii) patients with confirmed SAMS vs. non-SAMS.

Direct method:

Adherence to study treatment will also be determined directly in blood at the end of each treatment period with our liquid chromatography–tandem mass spectrometry method¹² classified according to the algorithm published by Kristiansen et al.¹⁵.

Adherence = patients being classified as non-adherent to atorvastatin in the end of the placebo study period *and* adherent to atorvastatin therapy in the end of the atorvastatin study period according to Kristiansen et al.¹⁵.

Low adherence = all patients not classified as adherent as defined above.

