3.2.2 Protocol Deviations

The following are pre-defined major protocol deviations regarded to affect the efficacy of the intervention:

- Entering the trial when the eligibility criteria should have prevented trial entry
- Discontinuation of intervention before 3 weeks in any treatment period
- Major change in concomitant lipid lowering medication reported by the patients
- Use of prohibited rescue medication
- Received or used other intervention than allocated

Protocol deviations are classified prior to unblinding of treatment. The number (and percentage) of patients with major and minor protocol deviations will be summarised with details of type of deviation provided.

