3.3 Analysis Populations

The Enrolled set will include all patients who have provided informed consent and have been included into the study data base.

The Full Analysis Set (FAS) will be defined as all patients randomly assigned to a treatment group having completed at least three consecutive study weeks on each treatment period.

The Safety Analysis Set will include all patients having received at least one study treatment tablet after randomisation.

The Per Protocol Analysis Set (PPS) will include all randomised patients meeting the study eligibility criteria and with no major protocol deviations affecting the treatment efficacy (i.e. <10% missing data* in the patient diary and >80% tablet adherence in the drug and placebo period, separately), and also being classified as non-adherent to atorvastatin in the end of the placebo study period by direct blood

STATISTICAL ANALYSIS PLAN for MUScle Side-Effects of atorvastatin in coronary patients (MUSE) – a randomized controlled trial

sample measurement according to Kristiansen et al.¹⁵. Patients being classified as partial adherent or non-adherent to atorvastatin therapy in the end of the atorvastatin study period by direct blood sample measurement (Kristiansen et al.¹⁵) will be excluded from the data analyses concerning blood levels of parent drug and metabolites.

**The percentage of missing data for the core self-reported variables in the diary (i.e. the VAS 0-10 cm likert scale and the 0-10 numeric rating scale) will be reported.*

4 Trial Population

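### Pill-count adherence divides by all tablets delivered, so a patient who misses no due tablet but ends a period early, as the SAP accepts, can be scored low-adherent and lost from the per-protocol set

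*SAP*

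**What the plan says.** **The adherence rule.** SAP 3.2.1 defines pill-count adherence, which it labels a proportion of days covered, as one minus remaining pills over the "number of pills delivered to patient". It then sets "Low adherence = PDC <80% in at least one of the two treatment periods". Mean adherence and the share of patients below the cut-off are to be shown overall and "stratified for (i) treatment order allocation and (ii) patients with confirmed SAMS vs. non-SAMS". Adherence is a named secondary objective (1.2.2) and secondary outcome (5.3.4).

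**The per-protocol rule.** SAP 3.3 makes ">80% tablet adherence in the drug and placebo period, separately" a condition for the PPS. The PPS is used for a secondary or sensitivity analysis of the primary outcome (6.3, 6.7).

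**Early end of a period.** Four places accept a period that ends from three weeks on:
- 2.7 says that V2 and V3 "may be scheduled after a treatment period of at least three consecutive study weeks (21 days) in participants with intolerable muscle complaints".
- 3.2.2 lists as a major deviation only "Discontinuation of intervention before 3 weeks in any treatment period".
- 3.3 puts in the full analysis set (FAS) all randomised patients "having completed at least three consecutive study weeks on each treatment period".
- 5.1.1 scores the last three completed weeks for patients who stop because of intolerable symptoms.

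**The concern.** A patient who stops at day 21 or later for intolerable muscle symptoms returns the tablets that were meant for the rest of the period. Those tablets were never due, so they are not missed doses. The formula in 3.2.1 nevertheless counts them against the patient, because no count of days enters it and no passage adjusts the denominator. The SAP thus accepts the stop in four places and can penalise it in a fifth.

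Two results are at stake. The PPS analysis is meant to test how robust the primary result is, but it could drop patients because of muscle symptoms, which are what the trial measures. The adherence table by statin-associated muscle symptom (SAMS) status could report symptom-driven stopping as poor tablet-taking.

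**Working it through.** The SAP gives no worked adherence figure and no supply, so there is no figure of its own to reproduce. The check applies its formula to a patient who takes every due tablet.

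**Inputs from the SAP**
- Planned treatment period: 7 weeks = 49 days (5.1.4, 5.1.5, 7).
- Earliest accepted end for intolerable symptoms: day 21 (2.7).
- Cut-offs: below 80% in either period is low adherence (3.2.1); above 80% in each period is needed for the PPS (3.3).

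**Assumptions, not in the SAP**
- One tablet daily and no missed dose up to the stop.
- S tablets delivered for the period by the time of the stop, shown for S = 28, 42, 49 and 56.

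**Formula.** With a stop at day d, tablets taken = d and remaining = S − d, so adherence = 1 − (S − d)/S = d/S. The PPS condition holds if d/S > 0.80, that is d > 0.8 × S, or equivalently S < 1.25 × d.

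| Delivered S | Stop day 21 | Stop day 28 | Stop day 35 | 0.8 × S | First passing day |
|---|---|---|---|---|---|
| 28 | 21/28 = 75.0% | 28/28 = 100% | supply used up | 22.4 | 23 (23/28 = 82.1%) |
| 42 | 21/42 = 50.0% | 28/42 = 66.7% | 35/42 = 83.3% | 33.6 | 34 (34/42 = 81.0%) |
| 49 | 21/49 = 42.9% | 28/49 = 57.1% | 35/49 = 71.4% | 39.2 | 40 (40/49 = 81.6%) |
| 56 | 21/56 = 37.5% | 28/56 = 50.0% | 35/56 = 62.5% | 44.8 | 45 (45/56 = 80.4%) |

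On the last failing days, 39/49 = 79.6% and 44/56 = 78.6%.

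**Largest supply at which the patient still passes (S < 1.25 × d)**
- Day 21: 1.25 × 21 = 26.25, so 26 tablets (21/26 = 80.8%; 21/27 = 77.8% fails).
- Day 28: 1.25 × 28 = 35, so 34 tablets. With 35 the score is exactly 80.0%, which fails the PPS cut-off but is not low adherence under 3.2.1.
- Day 35: 1.25 × 35 = 43.75, so 43 tablets.
- Day 42: 1.25 × 42 = 52.5, so 52 tablets.

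**One patient under each rule.** Take a stop at day 21, every tablet taken, 49 delivered, and the other period completed. The stop is not a major deviation (3.2.2), the patient is in the FAS (3.3), and the primary outcome is scored (5.1.1). The same patient is low-adherent (3.2.1) and outside the PPS (3.3).

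**With tablets due as the denominator.** Tablets due by day 21 = 21, so adherence = 21/21 = 100%, and d/d = 100% for any later stop.

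**The case against.** **The supply is unknown.** The misclassification needs S of at least 1.25 × d, and the SAP gives neither supply, tablets per day nor dispensing pattern, which may properly sit in the protocol. If tablets are handed out in short instalments, the problem shrinks or disappears. This stands as a limit on certainty. It does not rescue the formula: a supply near 7 weeks fails every stop in the first five weeks, and even 28 tablets fail a day-21 stopper.

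**A PPS may be strict on purpose.** The tablet cut-off in 3.3 can be read as an added condition on top of 3.2.2, and a sponsor may want near-full exposure. That is a legitimate choice, but the SAP does not state it; its only explicit discontinuation limit is three weeks. Exclusion for short exposure should not arise as a by-product of a denominator and carry the label of low adherence.

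**There are safeguards.** Blood-based adherence does not depend on tablets delivered, discontinuation for intolerable symptoms is reported (5.3.6), and the flow diagram gives reasons (4.1). These help a reader interpret the adherence table. They do not change PPS membership, because 3.3 adds the blood criterion to the tablet criterion and does not substitute one for the other.

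**Two stronger readings are not supported.**
- A reader might infer that the condition "<10% missing data* in the patient diary" excludes early stoppers in the same way. The SAP does not say that entries after an accepted stop are due, and in ordinary usage an entry that was not due is not missing.
- A reader might infer that the PPS estimate will be pulled towards no effect. Removing patients lowers the mean only if their average difference exceeds the mean of the whole set. The SAP does not say how many will stop, on which treatment, or with what differences.

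**Conclusion.** The concern holds for the pill-count denominator. As written, 3.2.1 gives a wrong adherence value for a patient who takes every due tablet and then stops as the SAP accepts, unless the supply delivered by then is less than 1.25 times the tablets due. With one tablet daily and 49 delivered, the score is 42.9% at day 21 and every stop before day 40 fails; with 56, every stop before day 45 fails. These figures rest on the assumed supply and daily count.

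The consequence is confined to the PPS analysis of the primary outcome and the descriptive adherence results. The primary analysis on the FAS is unaffected. The number of patients involved, and the direction and size of any PPS shift, cannot be stated from the SAP. It should be corrected, but it does not threaten the main result.

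**What to change.** - In 3.2.1, define adherence in each period as tablets taken (delivered minus returned) divided by tablets due from first dose to the recorded end of treatment in that period.
- Use this value in both the low-adherence definition in 3.2.1 and the PPS condition in 3.3, and treat exactly 80% the same way in both.
- If the sponsor does want shortened exposure out of the PPS, reconcile 3.2.2 with 3.3 and state it as a criterion of its own, not as low adherence.

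The cost is SAP wording, settled before unblinding as 3.2.2 already requires for classifying deviations. The new denominator needs the first-dose and end-of-treatment dates for each period. The three-week rules in 3.2.2, 3.3 and 5.1.1 already depend on how long each patient was treated, so little or no extra data should be needed. If the exact last-dose date was not recorded, the SAP should say which recorded date stands for the end of treatment.

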3.2.2 Protocol Deviations

The following are pre-defined major protocol deviations regarded to affect the efficacy of the intervention:

- Entering the trial when the eligibility criteria should have prevented trial entry
- Discontinuation of intervention before 3 weeks in any treatment period
- Major change in concomitant lipid lowering medication reported by the patients
- Use of prohibited rescue medication
- Received or used other intervention than allocated

Protocol deviations are classified prior to unblinding of treatment. The number (and percentage) of patients with major and minor protocol deviations will be summarised with details of type of deviation provided.

